9.9. Planned subgroup analyses

Subgroup analyses will be limited to the same variables used as minimisation variables (please refer to Section 4.6; excluding centre). Tests for statistical heterogeneity (e.g. by including treatment group by subgroup interaction parameter in the final regression model) will be performed prior to any examination of effect estimate within subgroups. The subgroup defined by gestational age (<70, ≥70 days) is of special interest; the results of other subgroup analyses will be treated with caution, and used for the purposes of hypothesis generation only.¹⁴ Analysis will be limited to the primary outcome measure only.

The effects of these subgroups will be examined by log-binomial regression model analysis, using independent variables as the interaction between treatment arm and each of the binary minimisation covariates (maternal age, BMI, previous parity, gestational age and amount of bleeding), separately for each subgroup analysis, together with their main effects. Where applicable, maternal age, body mass index and gestational age will be treated as continuous. The model will be adjusted for the clustering effect of randomising centres by using robust standard errors at centre level. The risk ratios and 95% confidence intervals and p-values for the interaction terms from the associated models will be presented. No adjustment for multiple testing will be made to the p-values for the interaction terms as we have pre-specified a subgroup of special interest and the results of all other subgroups analyses will be considered cautiously.

A template for reporting subgroup analyses is given in Appendix D8.

Sub-group related estimates and 95% confidence intervals may also be presented on a forest plot (see Figure 3).

9.10. Sensitivity analyses

Sensitivity analyses will be limited to the primary outcome and will consist of:

- a restricted analysis excluding women for whom the primary outcome was determined using information from the BERC review (i.e. women with available USS information only), to assess the robustness of the results that include clinical criteria for the primary outcome derivation.
- a multiple imputation approach¹⁵ if the missing primary outcome data is >5% (i.e. after using BERC information to derive the primary outcome). Women in the MifeMiso

combination group and misoprostol alone group will be imputed separately, which would allow unbiased estimates for any interaction effects between the treatment and covariates in the analysis model. The imputation model will include all the minimisation variables: maternal age, body mass index, previous parity, gestational age, amount of bleeding and randomising centres where maternal age, body mass index and gestational age will be treated as continuous and be used to generate 20 simulated data-sets. Analyses will then be performed on each set with the results combined using Rubin's rules¹⁶ to obtain a single set of results (treatment effect estimate and confidence intervals).

A template for reporting subgroup analyses is given in Appendix D6.

10. Analysis of sub-randomisations

Not applicable.

11. Health economic analysis

As indicated in the protocol there will also be a cost effectiveness analysis, based on the outcomes of cost per successfully managed miscarriage and cost per Quality-Adjusted Life Year (QUALY). The details of this analysis will be documented separately (see current version of the MifeMiso Protocol).

12. Statistical software

Stata version 12 (or higher) and/or SAS software, version 9.4 (or higher) will be used for all analyses.

13. References

1. Health and Social Care Information Centre. Hospital episode statistics. NHS maternity statistics 2011-12. <https://catalogue.ic.nhs.uk/publications/hospital/maternity/nhs-matereng-2011-2012/nhs-mate-eng-2011-2012-rep.pdf>.
2. NICE Clinical Guidelines [CG154]. Ectopic Pregnancy and miscarriage: diagnosis and initial management. December 2012.

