4.7. Sample size

We plan to randomise 710 women, 355 participants in each group. 670 women will need to be evaluated to detect a Minimally Important Difference (MID) of 10% reduction in the rate of failure to spontaneously pass the gestational sac within 7 days (i.e. from 25% to 15%), assuming 90% power and a type I error rate of 5%. However, assuming and adjusting for a worst case

scenario of 5% attrition, the total number of participants required will be 710. The 25% [95% CI: 23% to 27%] control group estimate is taken from our systematic review (unpublished data) and the 10% MID was the most popular selection from our health professional survey (41% of those surveyed). The estimate of the control group rate will be monitored throughout the recruitment period by the independent DMC to ascertain if any deviations from this assumption will impact on the sample size calculation.

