9.3. Handling missing data

Every attempt will be made to collect full follow-up data on all study women and so it is anticipated that missing data will be minimal. Women with missing primary outcome data will not be included in the primary analysis in the first instance. This presents a risk of bias, and sensitivity analyses will be undertaken on the primary outcome measure⁸ to assess the possible impact of the risk and to make sure we are complying with the intention-to-treat principle.

The derivation of the primary outcome is based on information regarding passage of the gestational sac by USS at 6-7 days post randomisation, or self-report data reviewed by a Blinded End-point Review Committee if USS information is not available. A sensitivity analysis will be undertaken restricted to participants with available USS information only, to assess the robustness of the results that include clinical criteria for the primary outcome derivation.

See section 9.10 for further details regarding sensitivity analyses.

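### The only analysis that restores women with a missing primary outcome is conditional on more than 5% missing and assumes missing-at-random given the primary model's own covariates, so it cannot reveal arm-specific, outcome-dependent missingness

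*SAP*

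**What the plan says.** Section 9.5 makes the primary analysis complete-case. Section 9.3 acknowledges that this may bias the result and promises sensitivity analyses on the primary outcome, partly "to make sure we are complying with the intention-to-treat principle". That promise carries no threshold.

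Section 9.10 limits the sensitivity analyses to two, and Appendix D6 has rows for those two only:

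- **Scan-only analysis.** It drops the women classified by the Blinded Endpoint Review Committee (BERC). It tests how the outcome was ascertained and leaves out more women, so it does not address missing outcomes.
- **Multiple imputation.** It is run "if the missing primary outcome data is >5% (i.e. after using BERC information to derive the primary outcome"), separately by arm, with 20 data sets. On its predictors the plan says: "The imputation model will include all the minimisation variables: maternal age, body mass index, previous parity, gestational age, amount of bleeding and randomising centres". No variable measured after randomisation is listed.

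Section 9.1 puts the same minimisation variables in the primary model. Section 9.1 also lists centre, as a random effect, whereas section 9.5 handles centre through robust standard errors. Under section 9.5 the imputation model thus has one predictor that the analysis model lacks.

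Section 9.4 defines who is missing: women with no scan and no early surgery, and women whose last scan was early and still showed the sac, unless the BERC unanimously finds the information sufficient.

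Section 4.7 sets the scale: "We plan to randomise 710 women, 355 participants in each group", 670 of them to be evaluated, after allowing for a worst-case "scenario of 5% attrition, the total number of participants required will be 710".

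**The concern.** A missing-data sensitivity analysis should ask whether the conclusion survives if the missing women differ from the observed ones. This one cannot ask that. When only the outcome is missing and it is imputed from the covariates of the analysis model, there are two cases:

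- If missingness depends only on those covariates, the complete-case estimate is already approximately valid and imputation has nothing to correct.
- If missingness depends on the outcome itself, imputation inherits the complete-case bias.

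Agreement between the two results is built in and is not evidence of robustness. At 35 or fewer missing women even this analysis is not run.

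Dependence on the outcome is plausible from the SAP's own coding. The women left as missing after BERC review can include some with no scan, who may well have passed the sac, and some with the sac still present on an early last scan, who may well not have. What is at stake is the intention-to-treat claim for the primary test, which under section 5.2 also decides whether the key secondary outcome is tested.

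**Working it through.** **1. The plan's own sample size.** For 25% vs 15%, two-sided 5% and 90% power, with pooled variance under the null:

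n per arm = [1.960 × √(2 × 0.20 × 0.80) + 1.282 × √(0.15 × 0.85 + 0.25 × 0.75)]² / 0.10² = 334.2, so 335 per arm and 670 in all.

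670 / 0.95 = 705.3, so 706, against the 710 stated. The sample size reproduces and is not at issue.

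**2. Where the trigger falls.** 35/710 = 4.93%, so no imputation. 36/710 = 5.07%, so imputation runs. If exactly 670 of 710 are evaluable, 40/710 = 5.6% are missing and imputation runs.

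**3. Does the planned imputation move the estimate?** Simulation with 300 trials of 710 women per scenario: five covariates and ten centres; logistic imputation by arm from those covariates plus centre; 20 data sets; Rubin's rules. The analysis model was Poisson with robust standard errors, not clustered by centre. The missingness rates are assumptions.

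| Missingness | % missing | RR, full data | RR, complete case | RR, imputed |
|---|---|---|---|---|
| Depends on covariates | 9.1 | 0.605 | 0.610 | 0.617 |
| Combination arm: 25% of failures and 5% of successes missing; control: 8% of all | 7.9 | 0.591 | 0.482 | 0.490 |

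The correlation between the complete-case and imputed estimates was 0.99 in both scenarios. The mean absolute gap in log RR within a trial was about 0.02 (95th percentile 0.06 and 0.07), from imputation noise, by-arm terms and centre. In the second scenario imputation repeated almost all of the bias.

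**4. When is the complete-case estimate biased?** With true failure rate p, and proportions m_F of failures and m_S of successes missing:

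observed rate = p(1 − m_F) / [p(1 − m_F) + (1 − p)(1 − m_S)].

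Take true rates of 15% and 25% (RR 0.600):

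- m_S = 10%, m_F = 2% in both arms: 0.147/0.912 = 0.161 and 0.245/0.920 = 0.266; RR 0.605.
- m_S = 3%, m_F = 20% in both arms: 0.120/0.9445 = 0.127 and 0.200/0.9275 = 0.216; RR 0.589.
- First pattern in control, second in combination: 0.127/0.266; RR 0.477.

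Bias is slight under a common mechanism and large when the mechanism differs by arm.

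**5. What could stay hidden below the trigger?** Take 17 combination and 18 control women missing (35), so 338 and 337 observed, at exactly 15% and 25%: 50.7 and 84.25 failures.

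- Complete case: RR 0.60, p = 0.001.
- All missing combination women fail, all missing controls pass: (50.7 + 17)/355 = 19.1% vs 84.25/355 = 23.7%; RR 0.80, p = 0.13.

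The remaining cases use whole counts and log-scale Wald tests:

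| Observed failures | Assumed failure among missing (combination / control) | RR | p, complete case | p, all women |
|---|---|---|---|---|
| 51 vs 84 (about 15% vs 25%) | 100% / 0% | 0.81 | 0.002 | 0.14 |
| 51 vs 84 | 50% / 10% | 0.69 | 0.002 | 0.015 |
| 51 vs 84 | 100% / 100% | 0.67 | 0.002 | 0.003 |
| 57 vs 84 (about 17% vs 25%) | 50% / 10% | 0.76 | 0.011 | 0.064 |
| 63 vs 84 (about 18.5% vs 25%) | 100% / 100% | 0.78 | 0.049 | 0.060 |

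The failure rates among missing women and the smaller observed effects are assumptions.

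**The case against.** The other side has real points.

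- **A reader might infer that a trial that goes to plan has no missing-data analysis.** The document does not support that. With 670 of 710 evaluable, 5.6% are missing and imputation runs, and section 4.7 calls 5% a worst case. The gap is at 35 or fewer missing women.
- **A reader might infer that follow-up data on these women go unused.** They do not. The BERC reviews the data relevant to the primary outcome before a woman is left missing. What remains unused is evidence too weak for a unanimous decision. For the same reason, extra predictors in the imputation model may add only modestly: the most informative cases are probably already classified.
- **A reader might infer that the complete-case result is badly biased.** Nothing in the SAP shows this. The trial is double-blind and placebo-controlled, and no stated feature makes missingness run in opposite directions by arm. Under a common mechanism the bias is negligible (step 4), and at the design rates the 50% / 10% scenario stays significant.
- **Missing data are expected to be minimal (section 9.3), and a 5% threshold is partly a matter of preference.** This is fair, but section 9.3 promises the assessment without a threshold.

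None of this meets the central point: no specified analysis examines a departure from missing-at-random.

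**Conclusion.** The point holds as a limitation of the sensitivity analysis, not as evidence of bias in the result. Section 9.10 does not deliver the check that section 9.3 promises. At 35 or fewer missing women, no analysis includes those whose outcome is missing. Above that, the imputation nearly repeats the complete-case risk ratio (mean shift under 0.01), so its agreement would not bear on the bias in question.

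The size of any actual bias is unknown. It is small if missingness works alike in both arms and large only if it differs by arm. The move from p of about 0.001 to about 0.13 at 4.93% missing is an extreme bound. It rests on every missing combination woman failing and every missing control passing. With smaller observed effects, milder assumptions are enough to cross 0.05. The near-equality of imputed and complete-case results is structural and does not depend on the simulated missingness rates.

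**What to change.** In section 9.10:

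1. Remove the 5% condition, so that the missing-data sensitivity analysis is run whatever the percentage missing.
2. Pre-specify a delta-adjusted (tipping-point) analysis with a separate delta for each arm, including all randomised women whose data may be used. Report how far missing women would have to differ, by arm, before the primary conclusion changes.
3. Optionally, add follow-up data already collected to the imputation model: early scan result, surgery after day 7, further misoprostol and the day-21 pregnancy test. Do not add surgery within 7 days. It defines failure under section 9.4, so it would predict the outcome perfectly, and no woman with a missing outcome should have it.

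Add a row for the tipping-point analysis to Appendix D6. The cost is some SAP wording and a little more analysis work; no new data are needed.

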Appendix A – Deviations from SAP

This report below follows the statistical analysis plan dated <insert effective date of latest SAP> apart from the following:

Section of report not following SAP	Reason
<insert section >	<insert, e.g. exploratory analyses request by TMG>

Appendix B – Trial schema

◇ Primary outcome.

* If gestational sac has been passed before the scheduled time for misoprostol, misoprostol can be omitted

** If scan performed earlier than day 6-7 and sac passed then repeat scan at day 6-7 not required

[figure not shown]
*** According to clinical judgment

**** Advice: Avoid surgical evacuation unless clinically indicated

Appendix C – Schedule of assessments

Outcome assessed	When?	How?	By whom?	Protocol driven (PD) or Standard Practice (SP)
Baseline data: EQ-5D-5L questionnaire	Day 0	Face to face clinical appointment with participant	Self-administered questionnaire	PD
OA1: Clinical review	Day 4-5	Telephonic or face to face clinical appointment with participant	Local research nurse/midwife or doctor	SP and PD
OA2: Clinical review +/- pelvic ultrasound, to determine whether the gestation sac has been expelled.	Day 6-7	Face to face clinical appointment with participant	Local research nurse/midwife or doctor	PD (and SP in some hospitals depending on trust policy)
OA2: EQ-5D-5L questionnaire	Day 6-7	Face to face clinical appointment with participant	Self-administered questionnaire	PD
OA3: Pregnancy test	Day 21± 2 days (point of discharge for women with negative pregnancy test result)	Clinical records and/or telephonic interview or face to face clinical appointment with participant	Local research nurse/midwife or doctor	SP
OA3: EQ-5D-5L questionnaire	Day 21± 2 days (point of discharge for women with negative pregnancy test result)	Telephonic or face to face clinical appointment with participant	Self-administered questionnaire	PD
OA4: Final discharge	Upon discharge	From clinical records or interview with the participant	Local research nurse/midwife or doctor	SP
OA4: EQ-5D-5L questionnaire (if initial positive pregnancy test result) and patient satisfaction survey	Upon discharge	Telephonic or face to face clinical appointment with participant	Self-administered questionnaires	PD
OA4: Semi-structured qualitative interview	Within 6 weeks of discharge	Face to face, via telephone or via video call with participant	Qualitative/mixed-methods researcher	PD

Appendix D1 – CONSORT flow diagram

Appendix D2 – Baseline characteristics

		Mifepristone + Misoprostol (N=)	Placebo + Misoprostol (N=)	Overall (N=)
Minimisation variables				
Maternal age (years)	< 30	N (%)	N (%)	N (%)
	≥ 30	N (%)	N (%)	N (%)
	Mean (SD)	Mean (SD)	Mean (SD)	Mean (SD)
	Median [IQR]	Median [IQR]	Median [IQR]	Median [IQR]
BMI (kg/m²)	< 35	N (%)	N (%)	N (%)
	≥ 35	N (%)	N (%)	N (%)
	Mean (SD)	Mean (SD)	Mean (SD)	Mean (SD)
	Median [IQR]	Median [IQR]	Median [IQR]	Median [IQR]
Previous parity	Nulliparous	N (%)	N (%)	N (%)
	Parous women	N (%)	N (%)	N (%)
Gestational age (days)	< 70	N (%)	N (%)	N (%)
	≥ 70	N (%)	N (%)	N (%)
	Mean (SD)	Mean (SD)	Mean (SD)	Mean (SD)
	Median [IQR]	Median [IQR]	Median [IQR]	Median [IQR]
Amount of bleeding	PBAC score ≤2	N (%)	N (%)	N (%)
	PBAC score ≥3	N (%)	N (%)	N (%)
Other demographic and clinical characteristics				
Ethnicity	White	N (%)	N (%)	N (%)
	Black	N (%)	N (%)	N (%)
	Asian	N (%)	N (%)	N (%)
	Mixed	N (%)	N (%)	N (%)
	Other ethnic group	N (%)	N (%)	N (%)
	Missing	N (%)	N (%)	N (%)
Progesterone levels	Mean (SD)	Mean (SD)	Mean (SD)	Mean (SD)
	Median [IQR]	Median [IQR]	Median [IQR]	Median [IQR]
	Not measured	N (%)	N (%)	N (%)
	Missing	N (%)	N (%)	N (%)
Pregnancy-related pain score at randomisation¹	Mean (SD)	Mean (SD)	Mean (SD)	Mean (SD)
	Median [IQR]	Median [IQR]	Median [IQR]	Median [IQR]
	Missing	N (%)	N (%)	N (%)
Number of gestational sacs	1	N (%)	N (%)	N (%)
	2	N (%)	N (%)	N (%)
	≥3	N (%)	N (%)	N (%)
	Missing	N (%)	N (%)	N (%)
Days from date of US diagnosing missed miscarriage to randomisation	Mean (SD)	Mean (SD)	Mean (SD)	Mean (SD)
	Median [IQR]	Median [IQR]	Median [IQR]	Median [IQR]
	Not measured	N (%)	N (%)	N (%)
	Missing	N (%)	N (%)	N (%)
Current concomitant medication	Yes	N (%)	N (%)	N (%)
	No	N (%)	N (%)	N (%)
	Missing	N (%)	N (%)	N (%)
If Yes, name of medication	<Name 1>	N (%)	N (%)	N (%)
	<Name 2>	N (%)	N (%)	N (%)
	<Name 3>	N (%)	N (%)	N (%)
	<Name 4>	N (%)	N (%)	N (%)

MifeMiso Statistical Analysis Plan v1.0

		Mifepristone + Misoprostol (N=)	Placebo + Misoprostol (N=)	Overall (N=)
Medical history				
Diabetes	Yes	N (%)	N (%)	N (%)
	No	N (%)	N (%)	N (%)
	Missing	N (%)	N (%)	N (%)
Renal disease	Yes	N (%)	N (%)	N (%)
	No	N (%)	N (%)	N (%)
	Missing	N (%)	N (%)	N (%)
Cardiac disease	Yes	N (%)	N (%)	N (%)
	No	N (%)	N (%)	N (%)
	Missing	N (%)	N (%)	N (%)
Chronic hypertension	Yes	N (%)	N (%)	N (%)
	No	N (%)	N (%)	N (%)
	Missing	N (%)	N (%)	N (%)
Thyroid disease	Yes	N (%)	N (%)	N (%)
	No	N (%)	N (%)	N (%)
	Missing	N (%)	N (%)	N (%)
Cancer	Yes	N (%)	N (%)	N (%)
	No	N (%)	N (%)	N (%)
	Missing	N (%)	N (%)	N (%)
Other	Yes	N (%)	N (%)	N (%)
	No	N (%)	N (%)	N (%)
	Missing	N (%)	N (%)	N (%)
Number of previous pregnancies				
Live birth	0	N (%)	N (%)	N (%)
	1	N (%)	N (%)	N (%)
	...	N (%)	N (%)	N (%)
	Missing	N (%)	N (%)	N (%)
Stillbirth	0	N (%)	N (%)	N (%)
	1	N (%)	N (%)	N (%)
	...	N (%)	N (%)	N (%)
	Missing	N (%)	N (%)	N (%)
Miscarriage	0	N (%)	N (%)	N (%)
	1	N (%)	N (%)	N (%)
	...	N (%)	N (%)	N (%)
	Missing	N (%)	N (%)	N (%)
Ectopic pregnancy	0	N (%)	N (%)	N (%)
	1	N (%)	N (%)	N (%)
	...	N (%)	N (%)	N (%)
	Missing	N (%)	N (%)	N (%)
Molar pregnancy	0	N (%)	N (%)	N (%)
	1	N (%)	N (%)	N (%)
	...	N (%)	N (%)	N (%)
	Missing	N (%)	N (%)	N (%)
Termination	0	N (%)	N (%)	N (%)
	1	N (%)	N (%)	N (%)
	...	N (%)	N (%)	N (%)
	Missing	N (%)	N (%)	N (%)
Pregnancy of unknown location	0	N (%)	N (%)	N (%)
	1	N (%)	N (%)	N (%)
	...	N (%)	N (%)	N (%)
	Missing	N (%)	N (%)	N (%)

¹ 0-10, 0 indicates no pain, 10 indicates worst possible pain.

Appendix D3 - Description of interventions

		Mifepristone + Misoprostol (N=)	Placebo + Misoprostol (N=)
Mifepristone or placebo taken	Yes	N (%)	N (%)
	No	N (%)	N (%)
	If no, reason:		
	Woman changed her mind	N (%)	N (%)
	Sac already passed	N (%)	N (%)
	Other	N (%)	N (%)
Misoprostol taken	Yes	N (%)	N (%)
	No	N (%)	N (%)
	If no, reason:		
	Woman changed her mind	N (%)	N (%)
	Woman did not attend hospital	N (%)	N (%)
	Sac already passed	N (%)	N (%)
	Other	N (%)	N (%)
If Yes, route of administration of first dose of misoprostol	PV	N (%)	N (%)
	PO	N (%)	N (%)
	Sublingual	N (%)	N (%)
	Missing	N (%)	N (%)
Additional doses of misoprostal taken	Yes	N (%)	N (%)
	1 additional dose	N (%)	N (%)
	2 additional doses	N (%)	N (%)
	≥ 3 additional doses	N (%)	N (%)
	Mean (SD)	Mean (SD)	Mean (SD)
	Median [IQR]	Median [IQR]	Median [IQR]
	No	N (%)	N (%)
	Missing	N (%)	N (%)
If Yes, route of administration of first additional dose	PV	N (%)	N (%)
	PO	N (%)	N (%)
	Sublingual	N (%)	N (%)
	Missing	N (%)	N (%)
If Yes, dose of first additional dose (mcg)	Mean (SD)	Mean (SD)	Mean (SD)
	Median [IQR]	Median [IQR]	Median [IQR]
	Missing	N (%)	N (%)
If Yes, days since mifepristone/placebo of first additional dose	Mean (SD)	Mean (SD)	Mean (SD)
	Median [IQR]	Median [IQR]	Median [IQR]
	Missing	N (%)	N (%)

Appendix D4 – Adherence to treatment allocation by group

	Mifepristone + Misoprostol (N=)	Placebo + Misoprostol (N=)
Number adherent with treatment regime¹	N (%)	N (%)
Number non-adherent	N (%)	N (%)
Missing²	N (%)	N (%)

¹ Defined as taking the allocated mifepristone/placebo on day 0 and subsequently misoprostol on day 2 unless the gestational sac has been passed before the scheduled time for misoprostol; in the latter case, the patient will be deemed to be adherent to the trial medication as long as the allocated mifepristone/placebo is taken on day 0.

² Either the drug information was missing on day 0 or it was missing on day 2 if the allocated drug was taken on day 0. If the allocated drug was not taken on day 0 the woman will fall into the category of non-adherence.

Note: All figures presented are N (%) unless otherwise specified.

Appendix D5 – Protocol deviations by group

Protocol deviation	Mifepristone + Misoprostol (N=)	Placebo + Misoprostol (N=)
A		
B		
C		

Appendix D6 – Primary outcome results

	Mifepristone + Misoprostol (N=)	Placebo + Misoprostol (N=)	Adjusted risk ratio ¹ (95% CI)	P-value
Failure to pass the gestational sac spontaneously within 7 days after randomisation				
Primary analysis				
Yes ²	N (%)	N (%)		
No	N (%)	N (%)		
Missing	N	N		
Sensitivity analysis				
Excluding women requiring primary outcome information provided by Blinded Endpoint Review				
Yes ²	N (%)	N (%)		
No	N (%)	N (%)		
Multiple imputation				
Yes ²	N (%)	N (%)		
No	N (%)	N (%)		

¹Value <1 favours MifeMiso combination group. The risk ratio was adjusted for minimisation variables: maternal age, body mass index, previous parity, gestational age and amount of bleeding. The clustering effect of randomising centres was accounted for by using robust standard errors at centre level.

²“Yes” means failed to pass the gestational sac spontaneously within 7 days after randomisation.

Note: All figures presented are N (%) unless otherwise specified.

